### **Early completion criteria**

Subjects who achieve complete healing\* of the target pressure ulcer will complete the study early. Subjects who can complete the study early will undergo all tests scheduled for the End-of-Study (85d) visit and then complete the study.

(\* Complete healing: Defined as the condition with the epithelial tissue covering 100% of the study ulcer, no abrasion or ulceration, intact dermis and epidermis.)

---

## **6. Statistical Analysis Population**

---

Data obtained from subjects in this study will be analyzed as the SS(Safety Set) and the FAS(Full Analysis set).

- 1) In the SS(Safety set), data obtained from subjects who were enrolled in the study, had at least 1 application of the study device, and had at least 1 safety assessment will be analyzed.
- 2) In the FAS(Full analysis set), data obtained from subjects who were enrolled in the study, had at least 1 application of the study device and then had at least 1 available endpoint of main interest review will be included in analysis.

---

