14.1 Discontinuation and withdrawal criteria

In case of meeting the following criteria for study device discontinuation, application of the study device and the study should be discontinued, and the reason for discontinuation and findings should be recorded in the Case Report Form.

- Criteria for discontinuation of the study device application

- 1) Acute reactions (allergy, hypersensitivity reactions, etc.) to the study device

- 2) It is determined that continuation of the study is difficult due to an accidental intercurrent condition.
- 3) It is determined that continuation of the study is impossible due to worsening of the pressure ulcer (Stage 4 or higher).
- 4) Debridement was performed during the study, after the study device application.
- 5) Pregnant during the study period
- 6) It is otherwise determined by the investigator that continued application of the study device is not appropriate due to reasons such as serious malnutrition, etc.
- 7) It is determined by the investigator that study participation is not appropriate due to a “serious adverse event”.

“Serious adverse event” is an event, irrespective of a causal relationship with the study device, that is as follows:

- ① Results in death or is life-threatening
- ② Requires inpatient hospitalization or prolongation of existing hospitalization
- ③ Results in persistent or significant disability or dysfunction
- ④ Results in congenital anomaly or birth defect
- ⑤ Other medically important events as identified by the Investigator

In case of discontinuation due to worsening of a pressure ulcer, the treating physician will ensure safety of the patient with appropriate tests and treatment, equivalent to the case of an adverse event.

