15.1 General principles of result analysis

Data obtained from subjects in this study will be analyzed as the SS(Safety Set) and the FAS(Full Analysis set).

- 1) In the SS(Safety set), data obtained from subjects who were enrolled in the study, had at least

- 1 application of the study device, and had at least 1 safety assessment will be analyzed.
- 2) In the FAS(Full analysis set), data obtained from subjects who were enrolled in the study, had at least 1 application of the study device and then had at least 1 available endpoints of main interest review will be included in analysis.

Efficacy and demographics will be analyzed using the FAS and safety data will be analyzed using the SS.

For subjects with a missing value during the study or who are withdrawn from the study prior to study completion, efficacy analysis will be conducted by applying the LOCF (Last Observation Carried Forward), only in case such subjects have available endpoints of main interest assessment results after the investigational device application. However, in case of missing values for Other endpoints and safety endpoints, raw data will be used for analysis, without applying LOCF.

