### **7.1 Efficacy Endpoints**

#### **(1) Endpoints of main interest**

- ① Number of patients with complete healing# of ulcer within 12 weeks  
: Subjects who achieved complete healing and had early completion or completion at the end of 12

weeks will be included.

- ② Time to complete healing# of ulcer within 12 weeks

: Time to complete healing is calculated as the number of days from baseline (1d).

(# The definition of complete healing: Epithelial tissue covering 100% of the study ulcer, no abrasion or ulceration, intact dermis and epidermis)

- ③ Pressure ulcer size by each time point
- ④ Pressure ulcer size reduction rate based on a scale at each time point

Reduction Rate=

$$\frac{\text{Pressure ulcer size on 1d}^* - \text{Pressure ulcer size at each time point from 8d to End-of-Study}^{**}}{\text{Pressure ulcer size on 1d}} \times 100\%$$

\* Using a scale-based pressure ulcer area (cm^2) measured prior to the study device application

\*\* Using a scale-based pressure ulcer area (cm^2) without re-epithelization\*\*\* measured at each time point after the study device application

(\*\*\*Re-epithelization: New epithelial tissue covering the pressure ulcer, with no exudate, transudate, or avascular tissue)

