### Analysis of Efficacy Endpoints

#### (1) Analysis of endpoints of main interest

- ① For subjects achieving complete healing within 12 weeks, present frequency and percentage. Fisher's exact test will be performed to compare Medifoam and Betafoam treatment groups.
- ② For the time to 100% complete healing, analyze using the Kaplan-Meier method. Time table for subjects to 100% complete healing will be presented and the survival Plot will be shown as a figure. Subjects not achieving 100% complete healing within 12 weeks will not be considered for evaluation for end point of main interest though ulcer size reduction will be evaluated for those subjects.

- ③ For the pressure ulcer size by each time point, present the mean, median, min, max and standard deviation. t-test will be conducted to compare Medifoam and Betafoam, and paired t-test will be used to see the difference between each post visit and baseline(1d).
- ④ For the pressure ulcer size reduction rate, present the mean, median, min, max and standard deviation. t-test will be conducted to compare Medifoam and Betafoam.
- ⑤ For the analysis for efficacy, conduct sub-analyses by use of topical antibiotics and glucocorticoids for the pressure ulcer during the study. t-test will be performed to compare Medifoam and Betafoam, and paired t-test will be used to see the difference between post visits and baseline(1d).

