## 9. Handling Missing Values

---

---

For subjects with a missing value during the study or who are withdrawn from the study prior to study completion, efficacy analysis will be conducted by applying the LOCF (Last observation Carried Forward), only in case such subjects have available endpoints of main interest assessment results after the investigational device application. However, in case of missing values for other endpoints and safety endpoints, raw data will be used for analysis, without applying LOCF.

---

---

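### The FAS leaves out randomised subjects with no ulcer review after device application, so the complete-healing and early-completion percentages may be overstated

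*SAP*

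**What the plan says.** SAP 6 admits to the FAS enrolled subjects who "had at least 1 application of the study device and then had at least 1 available endpoint of main interest review". Protocol 15.1 uses the same rule: the subject "had at least 1 application of the study device and then had at least 1 available endpoints of main interest review". It then assigns the sets: "Efficacy and demographics will be analyzed using the FAS and safety data will be analyzed using the SS".

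For the healing endpoint, SAP 7.1 defines who counts: "Subjects who achieved complete healing and had early completion or completion at the end of 12" weeks. SAP 8 gives the summary: "For subjects achieving complete healing within 12 weeks, present frequency and percentage", followed by Fisher's exact test between the two dressings. The shells of Tables 0601 and 0704 have Yes, No and Total rows and a p-value, and both stand under the FAS. No healing analysis on all randomised subjects is planned.

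SAP 9 applies LOCF to the efficacy analysis, but "only in case such subjects have available endpoints of main interest assessment results after the investigational device application". Protocol 15.1 has the same restriction.

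On assessments at withdrawal, the double-asterisk footnote to the protocol's Schedule of study activities gives withdrawn subjects all the Visit 14 tests, which include ulcer size and healing status. Protocol 12.1.4, which describes Visit 14, names the End-of-Study visit and early completion of healed subjects and does not mention withdrawn subjects.

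**The concern.** Complete healing is a recorded event. A subject in whom no closure was ever recorded can be classed as not healed without a further measurement, whereas an ulcer-size reduction cannot be calculated without one. The FAS rule treats the two kinds of endpoint alike.

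It also treats similar subjects differently. A subject who stops just after an unhealed 8d review stays in the FAS and, through LOCF, counts as not healed. A subject who stops just before that review, with no later one, is not counted at all. The plan gives no reason for the difference.

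The exclusion depends on what happens after randomisation and can only remove subjects who would sit in the No row. The arm's percentage therefore rises or, with no healers, stays the same. With 10 per arm and no replacement, one subject is visible in the result. Protocol 5.1 says that a further trial will build on these results, so an inflated healing rate could carry forward.

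**Working it through.** The plan has no figure to reproduce: it states no healing rate, dropout rate, power or significance level for efficacy, and Protocol 9 says there was no formal sample size calculation.

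**Inputs from the documents**
- 10 randomised per arm, withdrawals not replaced (Protocol 9).
- First scheduled review after application at 8d, then weekly to 85d (Protocol 10.1).
- The baseline photograph is taken before application (Protocol 12.1.2), so it does not satisfy the post-application condition in the FAS rule.
- FAS denominator and Fisher's exact test (SAP 8 and the shells of Tables 0601 and 0704).

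**Assumed inputs:** x = number healed in an arm; k = randomised subjects in that arm with no review after application. The documents give neither, so a range is shown.

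**Who leaves the denominator**
1. No review after application: the FAS condition fails.
2. No post-application result to carry forward: LOCF does not apply.
3. The subject is therefore in neither the Yes nor the No row.
4. A withdrawn subject who has the Visit 14 tests does have a review, enters the FAS and counts as not healed. For that subject k is not increased.

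**Effect on the percentage**

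All randomised: x/10. FAS: x/(10-k). Ratio: 10/(10-k), that is 10/9 = 1.11, 10/8 = 1.25 and 10/7 = 1.43 for k = 1, 2 and 3.

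| Healed x | All randomised | FAS, k=1 | FAS, k=2 | FAS, k=3 |
|---|---|---|---|---|
| 0 | 0.0% | 0.0% | 0.0% | 0.0% |
| 3 | 30.0% | 33.3% | 37.5% | 42.9% |
| 4 | 40.0% | 44.4% | 50.0% | 57.1% |
| 5 | 50.0% | 55.6% | 62.5% | 71.4% |

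The same arithmetic applies to Table 0704, with x as the number of early completers.

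**Effect on the planned Fisher test (two-sided, assumed counts)**

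| All randomised | p | FAS | p |
|---|---|---|---|
| 6/10 v 1/10 | 0.057 | 6/9 v 1/10 (one dropped) | 0.020 |
| 5/10 v 1/10 | 0.141 | 5/8 v 1/10 (two dropped, same arm) | 0.043 |
| 8/10 v 2/10 | 0.023 | 8/10 v 2/8 (two dropped, other arm) | 0.054 |

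The last row shows that the p-value can move either way, depending on which arm loses subjects. The rows were chosen because they cross 0.05, a level the SAP does not state for the efficacy tests. They show what is possible, not what is likely.

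**The case against.** A reader might infer that anyone who fails in week 1 drops out of the denominator. The documents do not support that. Failing and being unassessed are different things, and the schedule footnote gives withdrawn subjects the Visit 14 tests. Protocol 12.1.4 does not cancel the footnote: its restriction to healed subjects qualifies early completion, a term that Protocol 14.2 reserves for healed subjects, and it is silent on withdrawals. Home visits and unscheduled visits further reduce the chance of having no review.

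A reader might also infer unequal loss, because one dressing contains iodine and a listed stopping reason is "Acute reactions (allergy, hypersensitivity reactions, etc.) to the study device". It is possible but not shown. A subject stopped for a reaction is known to the investigator and is likely to be seen, and known hypersensitivity to povidone-iodine is an exclusion criterion. The subjects most likely to have no review are those who die, are lost or refuse, and nothing in the documents says that these will differ by arm.

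Three further points carry weight. For a subject lost in week 1 the true 12-week status is unknown, so counting that subject as not healed is a convention and not an observation. The study is exploratory, and Protocol 16.2 says there will be no formal test; its conflict with the Fisher test in the SAP is a separate matter. Tables 0102 and 0103 show discontinuations and FAS exclusions by arm, so a reader could divide the Yes count of Table 0601 by the Randomized count of Table 0103.

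These points limit the size and certainty of the problem but do not remove it. Neither the footnote nor a home visit yields a review in a subject who has died, is lost or refuses. Tables 0102 and 0103 disclose the exclusion, but the printed percentage and p-value stay on the FAS.

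**Conclusion.** The point holds in a limited form. The FAS rule removes randomised subjects with no main-endpoint review after application, and LOCF does not restore them. The percentages in Tables 0601 and 0704 may therefore be overstated in an arm by a factor of 10/(10-k), and the Fisher tests use the same reduced denominators.

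The factor rests on 10 randomised per arm and on counting unassessed subjects as not healed. If k = 0 or nobody in the arm heals, the effect is zero. Because the documents give no rate of unassessed subjects, it cannot be said that the percentages will be overstated, nor that one arm will be affected more than the other. The Fisher results are illustrations with assumed counts and an assumed 0.05 level.

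Given the exploratory aim and the disclosure in Table 0103, this is an inexpensive improvement to the plan and not a fault that undermines the study.

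**What to change.** - In SAP 6 and 8, report Tables 0601 and 0704 on all randomised subjects and count anyone without recorded complete healing by Visit 14 as not healed. Label this as a conservative convention.
- Keep the FAS result as a sensitivity line in both tables. Keep the FAS for ulcer size and its reduction rate, where a measurement is needed.
- Make the matching change in Protocol 15.1 at the next amendment.
- Reconcile the schedule footnote with Protocol 12.1.4, so that the assessments of withdrawn subjects are stated once and consistently.

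Cost: SAP wording and one extra line in two tables, with no new data. The protocol wording needs IRB approval under Protocol 21.2, which is why it can wait for an amendment made for other reasons. The healing percentages may come out slightly lower, and a subject who healed after being lost would be counted as not healed.

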## **7. Analysis of endpoints**

---

### **7.1 Efficacy Endpoints**

#### **(1) Endpoints of main interest**

- ① Number of patients with complete healing# of ulcer within 12 weeks  
: Subjects who achieved complete healing and had early completion or completion at the end of 12

weeks will be included.

- ② Time to complete healing# of ulcer within 12 weeks

: Time to complete healing is calculated as the number of days from baseline (1d).

(# The definition of complete healing: Epithelial tissue covering 100% of the study ulcer, no abrasion or ulceration, intact dermis and epidermis)

- ③ Pressure ulcer size by each time point
- ④ Pressure ulcer size reduction rate based on a scale at each time point

Reduction Rate=

$$\frac{\text{Pressure ulcer size on 1d}^* - \text{Pressure ulcer size at each time point from 8d to End-of-Study}^{**}}{\text{Pressure ulcer size on 1d}} \times 100\%$$

\* Using a scale-based pressure ulcer area (cm^2) measured prior to the study device application

\*\* Using a scale-based pressure ulcer area (cm^2) without re-epithelization\*\*\* measured at each time point after the study device application

(\*\*\*Re-epithelization: New epithelial tissue covering the pressure ulcer, with no exudate, transudate, or avascular tissue)

## (2) Other endpoints

- ① PUSH reduction rate at each time point

$$\text{Reduction rate} = \frac{\text{PUSH score on 1d} - \text{PUSH score at each time point}}{\text{PUSH score on 1d}} \times 100\%$$

- ② Dressing change frequency during the entire study period

: Calculated as the additional dressing frequency beyond twice daily

- ③ Number of subjects with early completion due to complete healing during the study
- ④ Incidence of new infections at the pressure ulcer until Week 12 based on the CSSC

$$\text{Infection incidence} = \frac{\text{Number of subjects with at least 1 new infection}^{**} \text{ until Week 12, after the study device application}}{\text{Total number of subjects}} \times 100\%$$

(\*\* Infection: Presence of 'Purulent exudates' or 2 or more symptoms of the CSSC. However, for subjects with an infection at baseline, it is defined as development of an additional symptom other than those confirmed at baseline or recurrence of baseline-identified symptoms after being completely healed.)

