10.2 Investigational device application methods

[Investigational devices]

Medifoam[®] (Mundipharma)

Betafoam[®] (Mundipharma)

[General investigational device application method]

An appropriate type of the investigational device should be selected for the study ulcer size and it should be able to completely cover the target pressure ulcer. At every dressing change, record the selected investigational device size in the source document.

[Investigational device application sequence]

- ① Carefully wash the target pressure ulcer with normal saline.
- ② After washing, wipe the study ulcer for drying with sterilized gauze, if necessary. At this time, pay attention not to irritate the study ulcer.
- ③ Select a study device that is larger than the pressure ulcer, open the product packaging, take out the device using tweezers, and remove the release film. Directly cover the wound with the foam side without the release film, paying attention to completely cover the wound.
- ④ If necessary, fix around the edge of this product with surgical tape or Band-Aid while paying attention not to attach too tight to avoid skin irritation.
- ⑤ If there is a lot of exudate and a leak is likely to occur at the study ulcer, exchange the dressing more frequently than planned (twice weekly).

[Application frequency]

- Twice weekly

During the 12-week treatment period, dressing is performed twice weekly, but additional dressing changes are allowed, depending on the condition of the pressure ulcer, such as excessive exudates at the lesion. Nevertheless, the frequency of additional dressing is limited to twice per day. In case of additional dressing changes beyond twice weekly changes, the change frequency should be recorded in the Case Report Form.

On the weekly site visit days, the investigator (or clinical research coordinator) will change the dressing; on other occasions, the subject or guardian will perform self-dressing. The investigator (or clinical research coordinator) will train the subject or guardian on the dressing method at every visit.

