12.2.9 Self-dressing training and frequency review

As a subject is to perform dressing twice weekly by himself/herself or a guardian, the investigator (or clinical research coordinator) will train the subject or guardian on standard dressing for self-dressing at every visit. Depending on the condition of the pressure ulcer such as excessive exudates, a subject may conduct self-dressing more frequently than twice weekly. In case of conducting self-dressing beyond twice weekly, the subject should inform the investigator of the additional dressing frequency during the site visit, and the investigator will record the frequency of self-dressing beyond twice weekly in the Case Report Form.

Standard dressing method will be trained as follows.

- ① Carefully wash the target pressure ulcer with normal saline.
- ② After washing, wipe the study ulcer for drying with sterilized gauze, if necessary. In this process, pay attention not to irritate the study ulcer with the gauze.
- ③ Open packaging of the study device, take out the device using tweezers, and remove the release film. Directly cover the wound with the foam side without the release film, paying attention to completely cover the wound.
- ④ If necessary, fix around the edge of this product with surgical tape or Band-Aid while paying attention not to attach too tight to avoid skin irritation.
- ⑤ If there is a lot of exudate and a leak is likely to occur at the study ulcer, exchange the dressing more frequently than planned for self-dressing (once weekly).

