15.3 Analysis of efficacy endpoints

(1) Analysis of endpoints of main interest

- ① Number of patients with complete healing# of ulcer within 12 weeks
: Subjects who achieved complete healing and had early completion will be included.
- ② Time to complete healing# of ulcer within 12 weeks
: Time to complete healing is calculated as the number of days from baseline (1d).
(# The definition of complete healing: Epithelial tissue covering 100% of the study ulcer, no abrasion or ulceration, intact dermis and epidermis)
- ③ Pressure ulcer size reduction rate based on a scale at each time point

$$\text{Reduction rate} = \frac{\text{Pressure ulcer size on 1d}^* - \text{Pressure ulcer size at each time point from 8d to End-of-Study}^{**}}{\text{Pressure ulcer size on 1d}} \times 100\%$$

* Using a scale-based pressure ulcer area (cm²) measured prior to the study device application

** Using a scale-based pressure ulcer area (cm²) without re-epithelization*** measured at each time point after the study device application

(**Re-epithelization: New epithelial tissue covering the pressure ulcer, with no exudate, transudate, or avascular tissue)

- ① For subjects achieving complete healing within 12 weeks, present frequency and percentage.
 - ② For the time to 100% complete healing, analyze using the Kaplan-Meier method. Subjects not achieving 100% complete healing within 12 weeks will not be considered for evaluation for end point of main interest.
 - ③ For the pressure ulcer size reduction rate, present the mean and standard deviation.
- For the analysis for efficacy, conduct sub-analyses by use of local antibiotics and glucocorticoids for the pressure ulcer during the study.

(2) Analysis of other endpoints

- ① PUSH reduction rate at each time point

$$\text{Reduction rate} = \frac{\text{PUSH score on 1d} - \text{PUSH score at each time point}}{\text{PUSH score on 1d}} \times 100\%$$

- ② Dressing change frequency during the entire study period
: Calculated as the additional dressing frequency beyond twice weekly
- ③ Number of subjects with early completion due to complete healing during the study
- ④ Incidence of new infections at the pressure ulcer until Week 12 based on the CSSC

$$\text{Infection incidence} = \frac{\text{Number of subjects with at least 1 new infection** until Week 12, after the study device application}}{\text{Total number of subjects}} \times 100\%$$

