## 3. Study Design

---

[figure not shown]
This is a single-center, randomized, 2-arms, open-label pilot study.

Subjects who consent to the study will be assessed for eligibility with screening tests. Subjects can have a 2-week screening period.

After screening, subjects who meet the inclusion/exclusion criteria will apply Medifoam® or Betafoam® for 12 weeks, after randomization. Targeted subjects are outpatient clinic or hospitalized patients. Subjects will make once weekly site visits.

During the treatment period, dressing is performed twice weekly, but additional dressing changes are allowed, depending on the condition of the pressure ulcer, such as excessive exudates at the study ulcer. Nevertheless, the frequency of additional dressing is limited to twice daily. On the weekly site visit days, the investigator(or clinical research coordinator) will change the dressing; on other occasions, the subject or guardian will perform self-dressing. Subjects who achieve complete healing of the target pressure ulcer within 12 weeks will have early completion.

Efficacy assessment is conducted for a total of 12 times at a 1-week interval, after the investigational device application (8d, 15d, 22d, 29d, 36d, 43d, 50d, 57d, 64d, 71d, 78d, 85d). At each efficacy assessment, the investigator (or clinical research coordinator) should take a digital photograph of the target pressure ulcer and retain it as a source document.

---

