### Further Consideration

- In principle, the analysis shall follow the methods presented in Protocol No. BTF16-AP-401 and the general items regarding statistical analysis procedure shall be described.
- For continuous variables, Shapiro-Wilk test with p-value 0.05 will be used for normality test. t-distribution approximation method will be used for Wilcoxon rank sum test.
- Chi-square test will be used on half of Fisher's exact test in case when SAS 9.3 cannot handle the amount of test calculation.

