		Mean±Std	xx.xx±x.xx	xx.xx±x.xx	xx.xx±x.xx	
		Median	xx.xx	xx.xx	xx.xx	
		Min~Max	xx.xx~xx.xx	xx.xx~xx.xx	xx.xx~xx.xx	
	Visit4~Visit13	..(Middle Part Omitted)..				
	Visit14(85d±2d)	N	xx	xx	xx	0.xxxx*
		Mean±Std	xx.xx±x.xx	xx.xx±x.xx	xx.xx±x.xx	
		Median	xx.xx	xx.xx	xx.xx	
Min~Max		xx.xx~xx.xx	xx.xx~xx.xx	xx.xx~xx.xx		
Glucocorticoids Not used	Visit3(8d±1d)	N	xx	xx	xx	0.xxxx*
		Mean±Std	xx.xx±x.xx	xx.xx±x.xx	xx.xx±x.xx	
		Median	xx.xx	xx.xx	xx.xx	
		Min~Max	xx.xx~xx.xx	xx.xx~xx.xx	xx.xx~xx.xx	
	Visit4~Visit13	..(Middle Part Omitted)..				
	Visit14(85d±2d)	N	xx	xx	xx	0.xxxx*
		Mean±Std	xx.xx±x.xx	xx.xx±x.xx	xx.xx±x.xx	
		Median	xx.xx	xx.xx	xx.xx	
Min~Max		xx.xx~xx.xx	xx.xx~xx.xx	xx.xx~xx.xx		

Note) \*: t-test, ¥ : Wilcoxon rank sum test

7) Analysis of Other endpoints

Analysis Set: FAS

Table 0701 PUSH reduction rate at each time point compared to baseline

Time points		Medifoam	Betafoam	Total	P-value
Visit3(8d±1d)	N	xx	xx	xx	0.xxxx*
	Mean±Std	xx.xx±x.xx	xx.xx±x.xx	xx.xx±x.xx	
	Median	xx.xx	xx.xx	xx.xx	
	Min~Max	xx.xx~xx.xx	xx.xx~xx.xx	xx.xx~xx.xx	
	P-value(within)	0.xxxx			
Visit4~Visit13		..(Middle Part Omitted)..			
Visit14(85d±2d)	N	xx	xx	xx	0.xxxx*
	Mean±Std	xx.xx±x.xx	xx.xx±x.xx	xx.xx±x.xx	
	Median	xx.xx	xx.xx	xx.xx	
	Min~Max	xx.xx~xx.xx	xx.xx~xx.xx	xx.xx~xx.xx	
	P-value(within)	0.xxxx			

Note) \*: t-test, ¥: Wilcoxon rank sum test

Table 0702 Dressing change frequency per week during the entire study period for subjects on Medifoam

	Medifoam			
	Visits			
Number of Dressing Change per week	Visit3	Visit4	....	Visit14
None	N	N	N	N
One time	N	N	N	N
Two times	N	N	N	N
Three times	N	N	N	N
Four or more times	N	N	N	N
Total	N	N	N	N

Table 0703 Dressing change frequency per week during the entire study period for subjects on Betafoam

\*Same as 0702

Table 0704 Number of subjects with early completion due to complete healing during the study

		Medifoam	Betafoam	Total	P-value
		n(%)	n(%)	n(%)	
Early completion due to complete healing	Yes	xx(xx.xx%)	xx(xx.xx%)	xx(xx.xx%)	0.xxxx‡
	No	xx(xx.xx%)	xx(xx.xx%)	xx(xx.xx%)	
	Total	xx(xx.xx%)	xx(xx.xx%)	xx(xx.xx%)	

Note) ‡: Fisher's exact test

Table 0705 Number of subjects with CSSC signs and symptoms at each visit for subjects on Medifoam

CSSC signs and symptoms	Medifoam			
	Visit2	Visit3	....	Visit14
Increasing pain in the ulcer area	N	N	N	N
• Can't detect pain in ulcer area	N	N	N	N
• Have less pain now than in the past	N	N	N	N
• Intensity of pain remained the same	N	N	N	N

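### The SAP counts extra dressing changes from twice daily, whereas the protocol counts the same endpoint from twice weekly

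*SAP*

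**What the plan says.** Protocol 15.3 (2), item 2, defines the endpoint as "Calculated as the additional dressing frequency beyond twice weekly". SAP 7.1 (2), item 2, defines it as "Calculated as the additional dressing frequency beyond twice daily".

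Elsewhere the SAP points towards the protocol's version. Section 3 says "During the treatment period, dressing is performed twice weekly, but additional dressing changes are allowed", and mentions twice daily only as the ceiling on those additions. Section 11 says "In principle, the analysis shall follow the methods presented in Protocol No. BTF16-AP-401". Table 0702 has the row header "Number of Dressing Change per week" with bins from none to four or more, and Table 0703 copies it. Neither shell says whether the count is of all changes or only of extra ones. SAP 8 plans Fisher's exact test between the arms on this endpoint.

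The protocol has several rules for what goes into the CRF:

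- Section 10.2: "In case of additional dressing changes beyond twice weekly changes, the change frequency should be recorded in the Case Report Form".
- Sections 12.1.3 and 12.1.4: self-dressing in excess of once a week, taken from the diary.
- Section 12.2.9: "the investigator will record the frequency of self-dressing beyond twice weekly in the Case Report Form". Step 5 of the same section puts planned self-dressing at once a week.
- Synopsis, Dressing: record the frequency when the twice-per-day limit on additions is exceeded.

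**The concern.** The two derivations of one endpoint differ by a single word, and that word moves the counting threshold from two changes a week to two changes a day. An analyst who programs the SAP as written will report almost no additional dressing changes, whatever happened. If no subject exceeds two changes on any day, everyone falls in one category and the planned Fisher's exact test has nothing to compare. An analyst who reverts to the protocol gets a sensible count, but the output then contradicts the SAP's written derivation with no documented reason.

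A related risk lies upstream. If some subjects are recorded under 12.2.9 and others under 10.2 or 12.1.3, the raw counts are not comparable between subjects, and no correction to the SAP repairs that.

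**Working it through.** The plan states no figure to reproduce and gives no expected change frequency, so the cases below are illustrative.

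**Inputs.** Two scheduled changes a week (Protocol 10.2, SAP 3), one of them made at the weekly visit. Let c be all changes in a week and n_d the changes on day d.

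**Formulas, additional changes per week**

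- Protocol 15.3: max(0, c − 2)
- Protocol 12.1.3 and 12.1.4: max(0, (c − 1) − 1), which equals the 15.3 count and agrees with 10.2
- Protocol 12.2.9: max(0, (c − 1) − 2)
- SAP 7.1, counted day by day: sum over days of max(0, n_d − 2)
- SAP 7.1, read as a weekly total: max(0, c − 14)

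**Results when no day has more than two changes**

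| c | Protocol 15.3 | Protocol 12.2.9 | SAP 7.1 (either reading) |
|---|---|---|---|
| 3 | 1 | 0 | 0 |
| 4 | 2 | 1 | 0 |
| 5 | 3 | 2 | 0 |
| 6 | 4 | 3 | 0 |
| 7 | 5 | 4 | 0 |
| 14 | 12 | 11 | 0 |

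Over 12 weeks the threshold is 2 × 12 = 24 changes under the protocol and 2 × 7 × 12 = 168 under the SAP, a sevenfold difference.

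**When a day exceeds two changes.** Take daily counts 3, 1, 1, 1, 1, 0, 0, so c = 7. Protocol 15.3 gives 5. SAP 7.1 gives 1 counted day by day and 0 against a weekly threshold of 14, so its own literal count is not unique.

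**Effect of the twice-per-day limit, if it is kept.** If it covers all changes in a day, the day-by-day SAP count is always 0, while the 15.3 count can run from 0 to 12. If it covers only changes added to the schedule, a scheduled day can hold 1 + 2 = 3 changes, and the SAP count can reach 1 on each of the two scheduled days. A SAP count of 1 then needs at least 2 extra changes under 15.3, and a SAP count of 2, the maximum, needs at least 4.

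**Table bins.** Four changes a week fall in the top bin (four or more) if the shell shows totals, in the two-times bin if it shows additions under 15.3, and in the none bin under SAP 7.1. Two changes a week fall in the two-times bin as a total and in the none bin as additions.

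**Recording under 12.2.9.** It gives one change fewer than 15.3 in every week with at least three changes. With the bins read as additions, the subject drops one bin at 3 to 6 changes a week and stays in the top bin from 7 upward.

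**The case against.** The SAP largely resolves this itself. Section 11 defers to the protocol, section 3 states the twice-weekly plan, and the shells are per week, so a competent analyst would probably notice and use 15.3. The all-zero result requires ignoring all three. The word daily also has a visible source, namely the limit in SAP 3 and the synopsis recording sentence. As for the tables, both derivations describe additional changes, and bins of none and one suit that reading under a twice-weekly schedule. The comparability worry depends on a CRF that is not among the documents and may impose a single rule.

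Much of this stands as mitigation. The table labels are a point of clarity. The synopsis sentence does not say that recording happens only above the limit, so it can coexist with 10.2. The conflict within 12.2.9 is real, but its consequence is conditional. The main point is untouched: section 11 defers only in principle and does not correct an explicit derivation, and a limit on extra changes is not the baseline from which they are counted.

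**Conclusion.** The concern holds. SAP 7.1 contradicts Protocol 15.3 on the same endpoint and, taken literally, gives 0 wherever no day has more than two changes, against 1, 2, 5 or 12 under the protocol at 3, 4, 7 or 14 changes a week. The mismatch itself rests on no assumption. The sizes assume one site change a week and illustrative frequencies; the bin shifts under 12.2.9 also assume that the shells show additional changes, and the limit results assume that the limit is kept.

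Severity is minor. The effect is confined to one other endpoint and its Fisher's exact test in an exploratory pilot of 20 subjects. No healing, ulcer size or safety result depends on it.

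**What to change.** 1. In SAP 7.1 (2), item 2, change daily to weekly, to match Protocol 15.3.
2. Label the bins of Tables 0702 and 0703 as total or additional changes.
3. Use one counting rule for the CRF. The simplest is additional changes beyond two a week in total. It already fits Protocol 10.2, 12.1.3 and 12.1.4, and the diary items in schedule footnote 9, 12.1.2 and 12.1.3. The recording rule in 12.2.9 needs rewording, as does the synopsis sentence, so that it cannot be read as recording only above the daily limit. The equivalence with self-dressing beyond once a week assumes one site change a week, so it depends on how the sponsor settles the planned self-dressing frequency.
4. Separately, the sponsor must reconcile two conflicts, on which this review takes no side: schedule footnote 4 sets no limit on additional changes, while the synopsis, Protocol 10.1 and 10.2 and SAP 3 set one; and 12.2.9 gives two planned self-dressing frequencies.

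The SAP cost is one word and two labels. Changes to protocol wording also need ethics committee approval under Protocol 21.2. Recording every change instead would cost more, because the diary and CRF wording would have to change: most diary items ask for additional changes, while 12.2.12 asks for the frequency of self-dressing.
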